### 8.2.5 Day 15 (± 1 Day)

The following procedures will be performed:

- Review of diary
- Targeted and symptom-driven physical examination
- Vitals signs
- Concomitant medications (including vaccines) recording
- AE assessment
- Sample collection:
  - o Serum for humoral response
  - Nasopharyngeal swab

#### 8.2.6 Day 29 (± 3 Days)

The following procedures will be performed:

- Targeted and symptom-driven physical examination
- Vitals signs
- Concomitant medications (including vaccines) recording

- AE assessment
- Urine pregnancy test
- ECG
- Sample collection:
  - o Clinical laboratory tests (hematology, serum chemistry, urinalysis)
  - Serum for humoral response (including serum for additional assays [see Section 7.10.2 and the laboratory manual for details])
  - Nasopharyngeal swab

#### 8.3 Follow-up Period

## 8.3.1 Day 91 (± 10 Days)

The following procedures will be performed:

- Recording of immunosuppressive medications (see list in Appendix 3) and vaccines
- Assessment of SAEs, MAEs, and NCIs
- Sample collection:
  - Serum for humoral response
  - Nasopharyngeal swab

#### 8.3.2 Day 181 (± 10 Days)

The following procedures will be performed:

- Recording of immunosuppressive medications (see list in Appendix 3) and vaccines
- Assessment of SAEs, MAEs, and NCIs
- Sample collection:
  - Serum for humoral response

#### 9 ADVERSE EVENTS

#### 9.1 Definitions

#### 9.1.1 Adverse Event

An AE is any untoward medical occurrence in a patient or clinical investigation subject administered a pharmaceutical product and which does not necessarily have a causal relationship with this treatment. An AE can therefore be any unfavorable and unintended sign (including an abnormal laboratory finding), symptom, or disease temporally associated with the use of an IP, whether or not related to the IP.

The term AE is used to include any AE whether serious or nonserious.

#### 9.1.2 Medically Attended Adverse Event

An MAE is an AE resulting in hospitalization, emergency room visit, or visit to or from medical personnel (other than routine health care visits).

#### 9.1.3 New-onset Chronic Illness

An NCI is an AE that is new (ie, not present at baseline) and typically chronic. The eCRF will provide a field in which the Investigator will indicate whether or not the AE recorded is an NCI. Because of the significance of this designation for the subject's health and for evaluation of vaccine safety, NCIs are expected to be diagnoses, not symptoms, and the Investigator should record sufficient data in the source document to support the diagnosis.

#### 9.1.4 Serious Adverse Event

An AE or suspected adverse reaction is considered serious (an SAE) if, in the view of either the Investigator or Sponsor, it results in any of the following outcomes:

- Death
- Life-threatening (An AE is considered life-threatening if, in the view of either the Investigator or Sponsor, its occurrence places the patient or subject at immediate risk of death. It does not include an AE that, had it occurred in a more severe form, might have caused death.)
- Inpatient hospitalization or prolongation of existing hospitalization
- A persistent or significant incapacity or substantial disruption of the ability to conduct normal life functions
- A congenital anomaly/birth defect

Life-threatening means that the subject was at immediate risk of death at the time of the SAE; it does not refer to a serious AE that hypothetically might have caused death if it were more severe. Hospitalization does not include same day surgery, elective surgery, optional admission not

05 October 2017 Confidential Page 39 of 66

associated with a precipitating AE (ie, elective cosmetic surgery), or hospitalization planned before the start of the study for a pre-existing condition that has not worsened. Persistent or significant disability or incapacity means that there is a substantial disruption of a person's ability to carry out normal life functions.

Important medical events that may not result in death, be life-threatening, or require hospitalization may be considered serious when, based upon appropriate medical judgment, they may jeopardize the patient or subject and may require medical or surgical intervention to prevent one of the outcomes listed in this definition. Examples of such medical events include allergic bronchospasm requiring intensive treatment in an emergency room or at home, blood dyscrasias or convulsions that do not result in inpatient hospitalization, or the development of drug dependency or drug abuse.

If it is not certain that an event meets the above definitions of an SAE, contact the Medical Monitor to discuss.

#### 9.2 Reporting Responsibilities and Periods

It is the responsibility of the Investigator or Subinvestigator(s) to perform periodic assessment of AEs. AEs spontaneously reported by the subject or reported in response to an open question from the study personnel (eg, 'Have you had any health problems since the previous visit/you were last asked?') or revealed by observation will be recorded.

All AEs (including MAEs, NCIs, and SAEs) with onset after signing of the ICF until Day 29 will be recorded. Thereafter to the end of study, only MAEs, NCIs, and SAEs will be recorded. Data describing AEs will be recorded in the subject's medical and as appropriate, an SAE report form. SAEs will be reported to the Sponsor as described in Section 9.7.

## 9.3 Recording of Adverse Events

An AE should be recorded individually in the study subject's own words (verbatim) unless, in the opinion of the Investigator, clarification of the subject's verbatim language is necessary or the AEs constitute components of a recognized condition, disease, or syndrome. In the latter case, the condition, disease or syndrome should be named rather than each individual symptom. The AE term will subsequently be coded using MedDRA.

The AE term, date of AE onset, date of AE resolution (if applicable), severity, causality, action taken for the AE, outcome and whether or not the AE is an MAE, NCI, and or SAE will be recorded.

05 October 2017 Confidential Page 40 of 66

#### 9.4 Assessment of Adverse Events

## 9.4.1 Severity

The Investigator will grade severity of AEs in accordance with Toxicity Grading Scale for Healthy Adult and Adolescent Volunteers Enrolled in Preventive Vaccine Clinical Trials (Appendix 1). If an appropriate listing is not present in this table for an AE, the AE will be graded as follows:

- Grade 1 (Mild) No interference with daily activity
- **Grade 2 (Moderate)** Some interference with daily activity but medical intervention not required (eg, doctor visit and/or prescription medicine); over-the-counter medicine permitted
- **Grade 3 (Severe)** Prevents daily activity and requires medical intervention (eg, doctor visit and/or prescription medicine)
- Grade 4 (Potentially Life-threatening) Emergency room visit or hospitalization

#### 9.4.2 Relatedness (Causality)

The Investigator will assess causality (relationship to NasoVAX/placebo) of AEs as follows:

- **Related** Reasons to consider an AE related to treatment may include, but are not limited, to the following:
  - O Timing of the event relative to the administration of the IP
  - O Location of the AE relative to the site of IP administration
  - O Likelihood based on experience with similar products
  - A biologically plausible explanation based on the mechanism of action or mode of delivery of the treatment
  - The AE is repeated on subsequent treatments.
  - No other explanation is likely.
- Unrelated An AE with no temporal association with the IP but rather related to other etiologies such as concomitant medications or conditions or subject's known clinical state

## 9.5 Clinical Laboratory, Physical Examination, Electrocardiogram and Vital Sign Abnormalities

Any abnormal laboratory result, physical examination finding, ECG interpretation, or vital sign measurement considered clinically significant by the Investigator will be recorded as an AE. A clinically significant laboratory abnormality is a confirmed abnormality (by repeat test) that is changed sufficiently from screening/baseline so that in the judgment of the Investigator a change in management is warranted. This alteration may include monitoring the laboratory test further, initiating other diagnostic tests or procedures, changing ongoing treatment, or administering new treatment.

05 October 2017 Confidential Page 41 of 66

Whenever possible, the underlying medical diagnosis (eg, anemia) will be recorded as the AE term. Repeated additional assessments required to establish the significance and etiology of an abnormal result should be obtained when clinically indicated.

A reactogenicity event recorded on the diary will not be recorded as an AE unless it meets the criteria of an SAE.

#### 9.6 Pregnancy

Pregnancy itself is not regarded as an AE unless there is a suspicion that the IP may have interfered with the effectiveness of a contraceptive medication. Pregnancy in a subject's partner is not considered an AE. Congenital abnormalities/birth defects and spontaneous miscarriages should be reported and handled as SAEs. Elective abortions without complications should not be handled as AEs. The outcome of a pregnancy will be followed-up and documented even if the subject as withdrawn from the study. See Section 10 for further information on reporting of pregnancy.

An induced elective abortion to terminate a pregnancy without medical reason is not regarded as an AE. However, an induced therapeutic abortion to terminate a pregnancy because of complications or medical reasons must be reported as an SAE. The underlying medical diagnosis for this procedure should be reported as the SAE term. A spontaneous abortion in a study subject is always considered an SAE.

## 9.7 Reporting of Serious Adverse Events

SAEs must be reported to the Sponsor or designee within 1 business day of becoming aware of the event. If at the time the Investigator initially reports an SAE, the event has not resolved, the Investigator must provide a follow-up report as soon as it resolves (or upon receipt of significant information if the event is still ongoing).

After review of an SAE report, the Medical Monitor may request additional documentation (eg, clinic or hospital records or procedure reports).

#### 9.8 Follow-Up of Adverse Events

A subject who experiences any AE, whether serious or not serious, will be monitored at appropriate intervals and receive appropriate treatment and medical supervision as clinically indicated. All AEs must be followed until resolution/stabilization or until a time that is mutually agreed upon between the Medical Monitor and the Investigator. Clinically significant laboratory abnormalities should be confirmed within 48 hours or as soon as clinically indicated and then followed weekly or as clinically indicated until resolution.

05 October 2017 Confidential Page 42 of 66

#### **10 PREGNANCY**

The ICF will include information regarding reporting of pregnancy to the Sponsor and collection of information through the end of pregnancy that occurs in either a female subject or in a female partner of a male subject. If a female partner becomes pregnant, the Investigator will request consent from the partner to collect this information.

Any pregnancy in a subject or in a subject's partner and the subsequent outcome (spontaneous miscarriage, elective termination, ectopic pregnancy, normal birth, or congenital abnormality) will be reported to the Sponsor.

If a subject becomes pregnant during the study, she should be encouraged to complete all scheduled follow-up unless there is a medical contraindication.

05 October 2017 Confidential Page 43 of 66

#### 11 SUBJECT AND STUDY DISCONTINUATION

## 11.1 Subject Withdrawal from the Study

Subjects may be withdrawn from the study at any time for the following reasons:

- Withdrawal of consent
- Noncompliance with study requirements
- Loss to follow-up
- Death
- Investigator discretion
- Sponsor request
- Termination of the study by the Sponsor (see Section 11.3).

Subjects that are withdrawn from the study will not be replaced.

## 11.2 Procedures for Subjects Who Terminate the Study Early

Any subject who prematurely discontinues the study should be followed-up for at least 28 days after the last dose of any IP.

If a subject prematurely discontinues the study on or before Day 29, then the procedures listed for Day 29 visit (Section 8.2.6) should be performed at the Early Termination Visit. If the subject is unwilling to return to the site for a visit, site staff will contact the subject by telephone to collect information about any AEs that have occurred since the last visit.

If a subject prematurely discontinues the study after Day 29, site staff will contact the subject once by telephone to collect information about any MAEs, NCIs, or SAEs, that have occurred since the last visit.

#### 11.3 Study Discontinuation

The entire study may be discontinued by the Sponsor for reasons including, but not limited to, the following:

- An unexpected, significant, or unacceptable risk to the subjects enrolled in the study
- Lack of evaluable or complete data
- Decision to modify the NasoVAX development plan or to suspend or discontinue NasoVAX development
- Medical or ethical reasons affecting the continued performance of the study
- Difficulty in recruitment of subjects

05 October 2017 Confidential Page 44 of 66

## 12 STATISTICAL METHODS

This section includes a brief description of the statistical analyses that will be performed in this study. A detailed statistical analysis plan (SAP) will be written and finalized before database snapshot for the interim analysis. Any deviation from the SAP will be described in the Clinical Study Report (CSR). All descriptive statistical analyses will be performed using SAS statistical software Version 9.2 or higher, unless otherwise noted.

#### 12.1 Analysis Populations

The following analysis populations will be used:

- Safety Population: All subjects who provide informed consent, are randomized, and receive at least 1 dose of IP. The Safety Population will be used for all safety analyses and will be analyzed according to the treatment received.
- ITT Population: All subjects in the Safety Population who have HAI assay results on Day 1 and any postvaccination time point. The ITT Population is the secondary population for immunogenicity analyses and will be analyzed according to treatment as randomized.
- PP Population: All subjects in the Safety Population that received the assigned dose of the test article in accordance with the protocol; have HAI assay results on Days 1, 15, and 29; and had no major protocol deviations affecting the primary immunogenicity outcomes as determined by the Sponsor prior to database lock. The PP Population is the primary population for immunogenicity analyses and will be analyzed as randomized.

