# 6.4 Blinding and Unblinding

Investigators, subjects, and all study staff with direct subject contact will be blinded to assignment to NasoVAX or placebo. A designated unblinded pharmacist (or otherwise qualified person) at the site will assign the NasoVAX or placebo based on the block randomization table provided by the unblinded statistician and prepare the blinded syringe for dispensing to the subject. The individual performing these tasks will have no contact with the subjects and minimize contact with other site study personnel.

Unblinding of vaccine assignment is discouraged. In the event of a medical emergency, for which the identity of the assignment is critical to the care of a subject, the Investigator will call the Medical Monitor to discuss. In the event that unblinding is deemed necessary, a designated unblinded study team member will provide the assignment to the Medical Monitor who will provide the information to the Investigator.

Sponsor personnel and other members of the study team will have no access to data aggregated by treatment arm until after the interim analysis (see Section 12.10). Sponsor personnel and other members of the study team will have no access to any individual treatment assignment except as needed to satisfy requirements for prompt reporting of SAEs to Regulatory Authorities. In this case, unblinded data from an individual subject will be provided immediately to the Medical Monitor

05 October 2017 Confidential Page 29 of 66

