## 12.3 Subject Disposition

The number and percentage of subjects enrolled in the study, completing the study, and discontinuing the study will be presented in a tabular format. Reasons for discontinuation will also be summarized.

Listings of randomized subjects who did not receive the IP and of subjects with other important protocol deviations (to be defined in the SAP, will be provided).

05 October 2017 Confidential Page 45 of 66

All analysis populations will be defined, and full descriptions of each population will be provided.

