#### 12.8 Immunogenicity Analyses

Immunology analyses will be conducted using the ITT and PP Populations with primary conclusions drawn from the PP Population. Analyses based on the ITT Population will be undertaken and presented only if >5% of subjects in any 1 dose group were excluded from the PP Population. No imputation for missing data will be performed. Data will be transformed as appropriate prior to analysis.

Baseline is defined as the sample collected prior to IP administration on Day 1.

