#### 12.10 Interim and Final Analyses

One interim analysis of humoral immunogenicity data and safety data (including summaries of AE, reactogenicity, concomitant medications and vaccines, vital signs, ECG, and laboratory data and listing of any viral culture results) will be conducted when all data through the Day 29 visit are available, monitored, and confirmed by the Investigator for all subjects. The purpose of this review is to plan future studies and adjust the clinical development plan accordingly.

An unblinded team composed only of members not otherwise involved in the study, will perform the interim analysis. All other study personnel including Investigators and investigational site staff and Sponsor staff and contractors will remain blinded to individual treatment assignments until database lock for final analysis.

Safety and immunogenicity analyses from the interim review may be presented in an interim statistical report drafted by the Sponsor. Data therein will be used to support development and planning of future studies, and may be submitted to the Center for Biologics Evaluation and Research and other Regulatory Authorities as needed.

The final CSR will include all study data through the end of study.

05 October 2017 Confidential Page 49 of 66

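### The per-protocol judgment for Days 1 to 29 stays open until database lock, after the Sponsor may have seen Day 29 results by arm; it should be settled before the interim snapshot.

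*Protocol*

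**What the plan says.** All references are to the protocol.

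- **Section 12.1** makes PP the primary population for immunogenicity. Members must have received the assigned dose, have HAI results on Days 1, 15 and 29, and have "had no major protocol deviations affecting the primary immunogenicity outcomes as determined by the Sponsor prior to database lock".
- **Section 12.8** analyses immunogenicity "with primary conclusions drawn from the PP Population". It adds the ITT analysis only if more than 5% of a dose group is excluded from PP.
- **Section 12** says the SAP "will be written and finalized before database snapshot for the interim analysis".
- **Section 12.10** says the single interim analysis, which includes humoral immunogenicity, "will be conducted when all data through the Day 29 visit are available, monitored, and confirmed by the Investigator for all subjects". Personnel outside the unblinded team "will remain blinded to individual treatment assignments until database lock for final analysis". It also says: "Safety and immunogenicity analyses from the interim review may be presented in an interim statistical report drafted by the Sponsor".
- **Section 6.4** says: "Sponsor personnel and other members of the study team will have no access to data aggregated by treatment arm until after the interim analysis".
- **Section 12.3** leaves the definition of important protocol deviations to the SAP.

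**The concern.** The Sponsor decides which deviations remove a subject from PP, and the only deadline for that decision is database lock. If this is the final lock, the Sponsor may already know the Day 29 antibody results by arm while the decision on Day 1 to 29 membership is still open. The deviation judgment is the one discretionary PP criterion, so its timing relative to the results matters.

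Section 4.2.3 says HAI will be important in choosing the dose for further development, and Section 12.10 allows interim results to be used for planning and sent to regulators. The final report could then give Day 29 results on a different PP set from the one behind those interim results, changed after they were seen. Nothing in the protocol requires both versions to be shown.

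**Working it through.** The protocol gives no figure on this point; its sample-size statements concern adverse events and do not bear on it. The check is a comparison of passages, then arithmetic on timing and size.

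**1. Which lock?** Section 12 calls the interim cut a snapshot. The only other use of database lock, in Section 12.10, is tied to the final analysis. The deadline in 12.1 therefore most naturally means the final lock. If the interim cut was intended, the sentence is ambiguous and the same edit cures it.

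**2. What may the Sponsor know by then?** Section 6.4 bars arm-level data only until the interim is done, and Section 12.10 lets the Sponsor draft the interim report. Individual assignments stay masked, but cohorts are sequential and defined by dose (Section 4.1). A subject's dose level therefore follows from the cohort; only NasoVAX versus placebo, at 3:1, is hidden.

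**3. Is the late date needed for Days 1 to 29?** No. The scheduled PP inputs are the dose received and HAI on Days 1, 15 and 29. Section 12.10 holds the interim until data through Day 29 are available, monitored and confirmed for everyone.

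**4. Length of the open period.** For the last subject, the gap between the Day 29 (±3) and Day 181 (±10) visits is:

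- nominal: 181 − 29 = 152 days
- shortest: (181 − 10) − (29 + 3) = 139 days
- longest: (181 + 10) − (29 − 3) = 165 days

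The exposure is the part of this gap that follows the interim, plus the time to final lock. The protocol dates neither the interim nor the lock.

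**5. ITT trigger.** With 15 NasoVAX subjects per dose group (Table 1), one exclusion is 1/15 = 6.7%, above 5%, so ITT would be presented.

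**6. Effect on the seroconversion rate (SCR).** The protocol gives no expected SCR, so a range is assumed. With r seroconverters of 15, dropping k non-seroconverters changes r/15 to r/(15 − k). The intervals are exact (Clopper-Pearson) for r/15.

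| r/15 | exact 95% CI | k = 1 | k = 2 |
|---|---|---|---|
| 3/15 = 20.0% | 4.3% to 48.1% | 3/14 = 21.4% (+1.4) | 3/13 = 23.1% (+3.1) |
| 6/15 = 40.0% | 16.3% to 67.7% | 6/14 = 42.9% (+2.9) | 6/13 = 46.2% (+6.2) |
| 9/15 = 60.0% | 32.3% to 83.7% | 9/14 = 64.3% (+4.3) | 9/13 = 69.2% (+9.2) |
| 12/15 = 80.0% | 51.9% to 95.7% | 12/14 = 85.7% (+5.7) | 12/13 = 92.3% (+12.3) |

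Every shifted value lies inside the interval for the unshifted rate.

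**7. Effect on GMT.** Dropping one of 15 subjects whose titer is f-fold below the group GMT multiplies the GMT by f^(1/14). For assumed f = 2 this is 1.05, and for f = 16 it is 1.22, a rise of 5% to 22%.

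**The case against.** The strongest reply is that 12.1 sets an outer limit, not a date of decision. The interim reports humoral immunogenicity and PP is the primary population for it, so a PP set must exist before anyone outside the unblinded team sees results by arm. An SAP that froze that set at the snapshot would comply fully with 12.1, and the SAP must be final by then. Individual assignments stay masked until final lock, which is the usual safeguard. A late limit also has a purpose: HAI is summarised on Days 91 and 181, and Section 6.8.2 prohibits other influenza vaccines for 90 days and immunosuppressants throughout, so relevant deviations can arise after Day 29. Finally, a late change needs a major deviation, one exclusion already brings in ITT, and the endpoints are secondary and descriptive.

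Most of this stands as a limit on severity. It does not remove the point. No passage carries the interim set forward unchanged, and 12.1 as written allows revision after arm-level access. An earlier date in the SAP would be stricter than the protocol but would not correct the deadline that the protocol itself states. Masking of individual assignments is partial, because dose level follows from the cohort. Deviations after Day 29 justify a later judgment for Days 91 and 181, not for Days 1 to 29. The ITT safeguard leaves ITT secondary and can work in reverse: reinstating a group's only excluded subject removes that group's trigger.

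**Conclusion.** The point holds as a modest, avoidable risk. The stated deadline lets the Sponsor change Day 1 to 29 membership of the primary immunogenicity set after Day 29 results by arm may be known. This rests on reading the deadline as the final lock, which the protocol's own vocabulary supports but does not state.

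A single exclusion would move SCR by 1.4 to 5.7 points, and two from one group by 3.1 to 12.3. These figures depend on the assumed rates and on every excluded subject being a non-seroconverter. No error rate is involved. The interim results themselves would rest on a set made before arm-level access; what is exposed is the final report's account of the same visits.

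**What to change.** In Section 12.1, replace the reference to database lock with:

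> PP membership for analyses through Day 29 is determined at a blinded review before the interim database snapshot and is used for both the interim and final Day 1 to 29 analyses. If a Day 1 to 29 deviation is discovered later, the change and its reason are documented in the CSR and Day 29 results are shown with both the original and the revised set. Deviations arising after Day 29 affect only the Day 91 and Day 181 analyses and are judged by criteria written before the snapshot.

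The cost is three sentences and a deviation review brought forward to before the snapshot. PP membership may then differ between the analyses through Day 29 and those at Days 91 and 181, and a late discovery would need one extra set of Day 29 tables. Sample size and data collection do not change.
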